3.2 Inclusion Criteria

- (1) At least 19 years of age
- (2) Became pregnant in 2023

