4.2 Data Collection

Once consent has been obtained, the baseline survey will automatically be pushed to the participant. The baseline answers will determine if pregnancy and or vaccine outcome surveys are to be answered at the same time. A short follow-up questionnaire will be administered on December 1st 2023 and another on February 1st 2024 to capture changes in vaccination status, COVID-19 status, pregnancy outcomes or significant health events. The follow-up surveys will determine if/when outcome surveys need to be completed. If consent is withdrawn, the study will immediately cease for the participant. The survey modules are as follows:

1. Baseline survey: Pregnancy status, vaccination status, demographics, health history, COVID-19 history & pregnancy history - Administered at enrollment starting Sept 1, 2023 until Jan 31, 2024

2. Pregnancy Outcomes: Pregnancy & infant outcomes – Administered if pregnancy started in 2023 and are not currently pregnant

3. Vaccine Outcomes: Answered if a dose of a COVID-19 vaccine received during the current pregnancy

4. Vaccine Attitudes 1: Feelings, opinions & attitudes towards vaccines– Administered at end of surveys received at baseline

5. Vaccine Attitudes 2: Feelings, opinions, and attitudes towards the Respiratory syncytial virus (RSV) – Administered following the completion of Vaccine Attitudes 1

6. Follow-up survey: 2 time-based follow-up surveys administered on December 1st, 2023, and on February 1st, 2024 with reminders sent out periodically throughout study duration
7. Health Event: Significant health events resulting in a visit to the emergency department or hospitalization – Administered if triggered by Follow-up survey

In the event of an adverse reaction or major health event, the study team will contact a participant for further health information.

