Data collected from individuals who do not receive COVID-19 vaccines will act as an internal comparison group. We will also capture self-identified gender through our online demographics questionnaire and examine differences by gender. The module on COVID-19 vaccination history will include type of vaccine received, number of doses and dosing interval. Vaccine safety endpoints will be coordinated with the Canadian National Vaccine Safety Network (CANVAS) endpoints: adverse events as detailed in data collection forms, severity and duration of adverse event, resultant medical visits (including to emergency department) or hospitalization, and treatments administered.

Pregnancy and infant safety outcomes measured are key outcomes identified by the Pan-Canadian, surveillance CANCOVID-Preg team. These major pregnancy complications/outcomes include but are not limited to gestational hypertension, gestational diabetes, placental abruption, infant birthweight, preterm birth, NICU admission, congenital anomalies, spontaneous abortion or termination, and stillbirth or neonatal death. Postnatally, including infants of women vaccinated during lactation, infant SARS-CoV-2 infection, hospitalization, growth parameters, and neurodevelopment (hyper vigilance) will be ascertained.

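### The Pregnancy Outcomes survey is triggered by pregnancy status on the survey day, so a 2023 pregnancy that ended and was followed by another is not routed to it

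*Protocol*

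**What the plan says.** - **Eligibility** (Protocol 3.2) is a property of the person: "Became pregnant in 2023". Nothing says which pregnancy counts if there were two.
- **Pregnancy Outcomes module** (Protocol 4.2): "Administered if pregnancy started in 2023 and are not currently pregnant".
- **Vaccine Outcomes module** (Protocol 4.2): "Answered if a dose of a COVID-19 vaccine received during the current pregnancy".
- **Baseline survey** (Protocol 4.2) covers "Pregnancy status, vaccination status, demographics, health history, COVID-19 history & pregnancy history" and is "Administered at enrollment starting Sept 1, 2023 until Jan 31, 2024".
- **Follow-up surveys** (Protocol 4.2) go out on 1 December 2023 and 1 February 2024. They are short and are meant "to capture changes in vaccination status, COVID-19 status, pregnancy outcomes or significant health events". Their answers decide whether and when an outcome module is sent.
- **Safety outcomes** (Protocol 4.2) include "congenital anomalies, spontaneous abortion or termination, and stillbirth or neonatal death".
- **Analysis** (Protocol 4.5): adverse outcomes, including pregnancy-related ones, are compared between vaccinated and unvaccinated participants with time-varying Cox models.

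**The concern.** The outcomes belong to pregnancies, but the module that collects them is switched on by what the participant is on the day she answers. The second half of the trigger does not ask whether the 2023 pregnancy has ended. It asks whether she is pregnant now. The two agree for most participants and part company for someone who has conceived again.

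The gap is not spread evenly over outcomes. The sooner a pregnancy ends, the more time remains to conceive again before a survey, so the rule bears mainly on early losses. These are among the outcomes on which the vaccinated and unvaccinated are to be compared. A time-varying model also needs the date of the event and the date of the dose for the same pregnancy, and answers that were never requested cannot be recovered at analysis.

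**Working it through.** The plan states no figure on this point, so there is none to reproduce. The check is one of routing, followed by an illustration of size.

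**1. The trigger applied to each type of participant.** Both conditions must hold.

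| Situation on the survey day | Pregnancy started in 2023 | Not pregnant now | Module for the ended pregnancy |
|---|---|---|---|
| 2023 pregnancy continuing | yes | no | not sent, correctly |
| 2023 pregnancy ended, not pregnant again | yes | yes | sent |
| 2023 pregnancy ended, pregnant again | yes | no | **not sent** |
| As above, and the second pregnancy has also ended | yes | yes | sent, but the text does not say for which pregnancy |

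The third row is the defect. If that participant had a dose in the first pregnancy and none in the second, Vaccine Outcomes is not triggered for her either, because it refers to the current pregnancy.

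**2. Does the calendar allow it?**

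- *Before enrolment.* Qualifying conceptions start on 1 January 2023 and enrolment opens on 1 September 2023: 31 + 28 + 31 + 30 + 31 + 30 + 31 + 31 = 243 days. For someone enrolling on the last day, 31 January 2024, the span is 243 + 122 (September to December) + 30 = 395 days. Conception, early loss and a new conception fit within either span.
- *Between surveys.* The loss and a recognised new pregnancy must both fall between two consecutive surveys. From 1 September to 1 December is 30 + 31 + 30 = 91 days; from 1 December to 1 February is 31 + 31 = 62 days. Later enrolment shortens the first interval. Missing the December survey joins the two into 91 + 62 = 153 days.

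So the main route is a loss before enrolment. Loss during follow-up is a lesser route.

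**3. Why losses are picked out.** A pregnancy conceived in January 2023 and carried to term ends around autumn 2023, which leaves only a few months to be pregnant again by the last survey. A pregnancy conceived at the same time and lost in spring leaves far longer.

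**4. Size, on assumed values only.** Let L be the loss risk and q the share of those with a loss who are pregnant again at every survey after it. Neither is in the documents.

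Losses outside the module per 500 = 500 × L × q. Risk seen through the module = L × (1 − q), with all 500 kept in the denominator and other sources ignored.

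| L | q | Missed per 500 | Risk seen |
|---|---|---|---|
| 10% | 5% | 2.5 | 9.5% |
| 10% | 30% | 15 | 7.0% |
| 15% | 5% | 3.75 | 14.25% |
| 15% | 30% | 22.5 | 10.5% |
| 20% | 5% | 5 | 19.0% |
| 20% | 30% | 30 | 14.0% |

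The figure of 500 is the per-group size in Protocol 4.5, used here only for scale.

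**5. Effect on the comparison.** The ratio of module-captured risks equals the true ratio × (1 − q in the vaccinated) / (1 − q in the unvaccinated). Equal shares leave the ratio unchanged, and unequal shares can move it either way. The documents say nothing about q in either group.

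**The case against.** The strongest reply is that section 4.2 has other routes. Baseline takes a pregnancy history, and both follow-ups are meant to register changes in pregnancy outcomes and to decide which modules follow. A reader might infer from the trigger that such a loss is never recorded, or that the lost pregnancy is carried in the data as continuing. The documents do not support either inference. What they leave open is narrower. The only stated rule for sending the detailed module is the one that fails here. Nothing shown says that the history or the short follow-up obtains the date of loss, the gestational age or the timing of a dose.

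Second, the prospective case is narrow. A participant who loses a pregnancy on 20 September and answers on 1 December escapes the module only if she is again knowingly pregnant within 72 days (10 + 31 + 30 + 1). This stands, and it is why the weight falls on losses before enrolment.

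Third, vaccine exposure does not depend on the Vaccine Outcomes module alone: baseline asks for vaccination status, and a vaccination-history module records type, doses and interval. This also stands. What may go missing is the module's detail on that dose and its link to the ended pregnancy.

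Fourth, the trigger is one line, perhaps loosely put, and the questionnaires and branching logic are not shown. The built survey may do the right thing. That is a reason for moderate confidence, but it does not make the written rule correct.

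Fifth, the unit of analysis and the handling of repeated pregnancies are usual matters for an analysis plan. Agreed, and they are not part of this point. Whether the question is asked at all is a matter of data collection.

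**Conclusion.** The point holds in a limited form. As written, the protocol does not route an ended 2023 pregnancy to the Pregnancy Outcomes module when the participant is pregnant again, and Vaccine Outcomes has a parallel gap. The capture of spontaneous abortions and terminations may therefore be selectively incomplete, mostly for losses before enrolment. It is worth correcting because the gap arises at collection and the remedy is small.

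The size is not known. The 2.5 to 30 losses per 500 rest on assumed values of L and q, and on counting only what the module collects. A reader might go on to conclude that reported loss rates will be too low, or that the vaccinated-versus-unvaccinated ratio is biased in a particular direction. The first depends on what the baseline history and follow-up items obtain, which cannot be seen. The second depends on how re-conception differs by vaccination status, on which the documents are silent.

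**What to change.** 1. Reword the Pregnancy Outcomes trigger in section 4.2 so that the module is given for each pregnancy that began in 2023 and has ended, whether or not the participant is pregnant again, at baseline and at both follow-ups.
2. Add a question at each follow-up asking whether the pregnancy reported last time is the same one as now.
3. Trigger Vaccine Outcomes for a dose received in any pregnancy that began in 2023, and record which pregnancy it was.

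This takes changes to the branching conditions of two modules and one added question in the existing REDCap surveys. The downside is a slightly longer survey for the few participants with two pregnancies. How repeated pregnancies in one person are analysed can be left to the analysis plan. If the built survey already works this way, only the protocol wording needs to change.

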4.5 Statistical Analysis and Metrics

To adequately power for comparisons of adverse events, we used estimates of vaccine-related adverse events (i.e. pain at injection site, redness, swelling, fever, fatigue, chills, headache, muscle pain, joint pain, grade 4 serious adverse events) from the subset of younger participants in the Pfizer vaccine trial, as an example (12). The rate of overall adverse events was 25%, and with a sample size of 451 in the vaccinated cohort we could estimate this prevalence with $\pm 4\%$ precision and 95% confidence. Sample sizes are highly feasible and will allow for comparison of adverse obstetrical and infant outcomes between vaccinated and unvaccinated participants. Given a sample size of 500 per group (vaccinated vs. unvaccinated) we would have 80% power to detect a minimum relative risk of 1.5.

The immunogenicity sub-study would require 89 participants, assuming 10% loss to follow up to estimate a 70% seroconversion rate with \pm 10% precision and 95% confidence. A seroconversion rate closer to 80% would require 68 participants. For comparisons of antibody levels, using estimates for the 18-55y age group (13) we would need approximately 48 participants to demonstrate a 10% difference in geometric mean titer with 95% power and assuming an attrition rate of 10% per visit.

The presence of any adverse outcomes (vaccine and pregnancy-related) will be compared between vaccinated and unvaccinated using time-varying Cox's proportional hazards models (14), stratified by vaccine type, and including important confounders. Effectiveness will be assessed descriptively through participant reporting of positive SARS-CoV-2 tests and COVID-19 diagnoses in vaccinated

and unvaccinated participants. Clinical features of breakthrough cases will be described in those vaccinated. Exploratory analyses will investigate differences between vaccinated and unvaccinated people. Clinical severity will be compared with unvaccinated people in the CANCOVID-Preg cohort. This will include tracking of infections with variants of concern where possible in both vaccinated and unvaccinated participants.

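### Vaccine reactions are asked about at enrolment or on two calendar dates, never at a set time after the dose, so their prevalence is open to recall and truncation error that the ±4% does not cover

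*Protocol*

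**What the plan says.** Vaccine safety is the first of five primary objectives (Protocol 2.0). The adverse events used for its sample size are "pain at injection site, redness, swelling, fever, fatigue, chills, headache, muscle pain, joint pain, grade 4 serious adverse events" (4.5), mostly short local and systemic reactions. The safety endpoints in 4.2 include "adverse events as detailed in data collection forms, severity and duration of adverse event". Under 3.1, outcomes are self-reported online.

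Section 4.2 gives the module that collects them two routes:

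- **At enrolment**, on any day from 1 September 2023 to 31 January 2024: "The baseline answers will determine if pregnancy and or vaccine outcome surveys are to be answered at the same time".
- **After enrolment**, through the follow-up surveys: "A short follow-up questionnaire will be administered on December 1st 2023 and another on February 1st 2024". These decide whether and when an outcome module is due.

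The module's only condition is "Vaccine Outcomes: Answered if a dose of a COVID-19 vaccine received during the current pregnancy". No time since the dose is set as a trigger or a limit. Eligible pregnancies can start from 1 January 2023 (3.2).

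On precision, 4.5 takes an overall adverse-event rate of 25% and says that "with a sample size of 451 in the vaccinated cohort we could estimate this prevalence with" ±4% at 95% confidence.

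**The concern.** Injection-site pain, fever or chills must be caught while they can still be remembered, and after they have had time to appear and end. Here the gap between dose and question depends on when the participant enrolled and where the dose fell relative to two calendar dates. Two errors follow:

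- **Recall.** With a long gap, mild reactions may be forgotten, which lowers the rate. People who reacted badly may remember or attribute more, which raises it. Duration and severity are affected too.
- **Truncation.** Someone who answers on the day of the dose, or a day or two later, reports before a reaction has begun or ended.

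Neither error shrinks with more participants, and neither is in the confidence interval. Section 4.5 plans models stratified by vaccine type, so if types were given at different times relative to the surveys, the gap would differ between strata.

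**Working it through.** **1. The plan's own figure.** Inputs from 4.5: p = 0.25, d = 0.04, 95% confidence.

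n = 1.96² × 0.25 × 0.75 / 0.04² = 450.2, rounded up to 451. Half-width at 451 = 1.96 × √(0.1875/451) = 0.040. The stated figure is reproduced. It is a sampling-error calculation.

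**2. Longest gaps, from the dates in 3.2 and 4.2.**

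- Dose after enrolment: 1 September to 1 December is 91 days; 1 December to 1 February is 62 days.
- Dose before enrolment: 1 January to 1 September 2023 is 243 days. For someone still pregnant at a later enrolment, the limit is the length of pregnancy, assumed to be about 265 to 280 days.
- Shortest gap on either route: the same day.

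**3. Typical gap, doses after enrolment.** Assumptions: enrolment even over September to January, doses even up to 1 February, only doses after enrolment kept, surveys answered on the day they are sent. Let x be the dose day counted from 1 September, so 1 December is day 91 and 1 February day 153. The number already enrolled grows in proportion to x, so the share of doses between days a and b is (b² − a²)/153², with 153² = 23,409.

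| Gap | Dose days | Share |
|---|---|---|
| Over 28 days | 0–63 and 91–125 | (3,969 + 7,344)/23,409 = 48% |
| Over 56 days | 0–35 and 91–97 | (1,225 + 1,128)/23,409 = 10% |
| Under 7 days | 84–91 and 146–153 | (1,225 + 2,093)/23,409 = 14% |
| 7 to 42 days | 49–84 and 111–146 | (4,655 + 8,995)/23,409 = 58% |

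The mean gap is 10.7 days (doses before 1 December) + 18.3 days (doses after it) = 29 days, where each term is the integral of the gap × 2x/153². Late replies would lengthen these gaps.

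**4. Typical gap, doses before enrolment.** Assumptions: pregnancy starts even over 2023, enrolment even, dose even over the pregnancy so far, still pregnant at enrolment. Simulation gives a median of about 50 days, 46–47% over 56 days, and about 33% between 7 and 42 days. Allowing 280 days of pregnancy moves the median to 52 days.

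**5. What recall error could do.** The documents give no recall figure, so this is illustration only. With f the share of reactions not reported and g the share of reaction-free participants who report one, the expected estimate is 0.25(1 − f) + 0.75g. Coverage is how often the nominal 95% interval contains 25% at n = 451.

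| f | g | Expected estimate | Coverage |
|---|---|---|---|
| 5% | 0 | 23.75% | 90% |
| 10% | 0 | 22.5% | 75% |
| 16% | 0 | 21.0% | 45% |
| 20% | 0 | 20.0% | 24% |
| 30% | 0 | 17.5% | 1% |
| 0 | 5% | 28.75% | 58% |
| 10% | 5% | 26.25% | 91% |

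At f = 16% the bias equals the whole 4 points. The last two rows show that the error can also be upward or partly cancel.

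**The case against.** **The design is what it is.** An open, self-enrolled registry that admits people already vaccinated must rely on recall for them. That stands: no trigger shortens the gap for a dose given months before enrolment. It does not explain the absence of a dose-anchored question after enrolment, or the acceptance of answers given too early.

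**The forms or the SAP may deal with it.** The data collection forms and the SAP are not shown. The forms may define a post-dose window, and 4.2 already collects the dosing interval, so dose dates may be on file. An analysis window could sit in the SAP. This stands in part. When participants are asked, however, is fixed in 4.2, and neither a window nor an analysis recovers a forgotten reaction.

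**Other contacts exist.** Section 4.2 has the study team contact participants after an adverse reaction, but gives neither a timing nor a separate way of learning of the reaction. The 4- and 12-week post-vaccination visits in 4.3 are for blood samples, in the BC sub-study only.

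**Stronger readings that the documents do not support:**

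- A reader might infer that the estimate *is* biased, and downwards. Size and direction cannot be derived from the documents.
- A reader might infer a comparison of the observed rate with 25%, or of reactions by trimester. The protocol plans neither. The 25% is a planning input, and comparison with licensure data and stratification by gestational age belong to the immune sub-study (4.6).
- Taking doses as even from 1 September to 1 February gives 63% of gaps over 28 days, (63 + 34)/153, and 27% over 56 days, (35 + 6)/153. That requires everyone to enrol on 1 September.
- A reader might want the main estimate restricted to short recall. Only about 33% of pre-enrolment and 58% of post-enrolment doses fall 7 to 42 days before the survey, so the loss of precision could rival the bias removed.

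**Conclusion.** The point holds as a weakness in data collection, not as an error in the sample-size arithmetic. No contact is tied to the dose, and reports of brief reactions would be made anywhere from the same day to 91 days later (post-enrolment doses) or about 265 to 280 days later (pre-enrolment doses). The prevalence serving the first primary objective is therefore open to recall error of unknown size and direction, and to truncation in the roughly 14% of post-enrolment doses asked about within 7 days. The ±4% is right for sampling error and says nothing about either.

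The maximum gaps after enrolment follow from the protocol's dates alone. The typical gaps rest on the even-spread assumptions, and the pre-enrolment maximum on the assumed length of pregnancy. Serious events leading to an emergency visit or hospitalization are less exposed.

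**What to change.** **In 4.2:** record the date of each dose and of survey completion. When a dose was given less than 7 days before the survey, have REDCap send the Vaccine Outcomes module, or a repeat of it, once 7 days have passed. For the last survey this means about 8 February 2024 at the latest if it is answered on the day, inside the timeline to March 2024 in the Summary.

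**In 4.5:**

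- define the prevalence as events starting within a fixed window after the dose (for example 7 days);
- keep every dose whose window has closed in the main estimate;
- report the prevalence by dose-to-survey interval, with a short-recall (7 to 42 days) sensitivity estimate;
- state that ±4% covers sampling error only.

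A link that participants open themselves about a week after a dose is optional. Its reports should be flagged, because people who reacted may report first.

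**Cost:** a little survey set-up and analysis, with no change to the target of 451. The short-recall estimate is less precise. If 33% qualify (149 of 451), the half-width is 1.96 × √(0.1875/149) = ±7.0 points; if 58% qualify (262), it is 1.96 × √(0.1875/262) = ±5.2 points. It should therefore be a sensitivity estimate and not the main one.

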2.0 OBJECTIVES

Primary objectives:

1. To assess the safety of COVID-19 vaccines in pregnant and lactating individuals

2. To describe the effectiveness of COVID-19 vaccines in pregnant and lactating individuals

3. To examine attitudes towards COVID-19 vaccination, and other vaccinations, including RSV, among pregnant and lactating individuals

4. To examine the immunogenicity of COVID-19 vaccines within a subset of pregnant individuals and for their infants

5. To assess attitudes and the impact of co-administration of the COVID-19 vaccine with other regular vaccinations, such as the influenza vaccine, among pregnant and lactating individuals

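### Objective 1 covers vaccine safety in lactation, but the Vaccine Outcomes module is triggered only by a dose in the current pregnancy, so ordinary reactions after a lactation dose have no stated collection route

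*Protocol*

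**What the plan says.** Protocol section 2.0 gives as its first primary objective "To assess the safety of COVID-19 vaccines in pregnant and lactating individuals". Section 3.2 sets two inclusion criteria, a minimum age and "2) Became pregnant in 2023", so people whose 2023 pregnancy has already ended can enrol.

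Section 4.2 lists seven survey modules. Four matter here:

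- **Baseline survey:** "Administered at enrollment starting Sept 1, 2023 until Jan 31, 2024".
- **Pregnancy Outcomes:** "Administered if pregnancy started in 2023 and are not currently pregnant".
- **Vaccine Outcomes:** "Answered if a dose of a COVID-19 vaccine received during the current pregnancy".
- **Health Event:** "Significant health events resulting in a visit to the emergency department or hospitalization", opened only if a follow-up survey triggers it.

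On routing, the same section says: "The baseline answers will determine if pregnancy and or vaccine outcome surveys are to be answered at the same time". Follow-up surveys on 1 December 2023 and 1 February 2024 record changes in vaccination status, COVID-19 status, pregnancy outcomes and significant health events, and decide whether outcome modules are needed. The study team is to contact a participant after an adverse reaction or major health event.

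Later in section 4.2 the safety endpoints are set out: adverse events with their severity and duration, resulting medical visits or admissions, and treatments. Infant outcomes are to be ascertained postnatally, "including infants of women vaccinated during lactation".

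**The concern.** The objective and the safety endpoints cover people vaccinated while lactating, but the module that asks about reactions to a dose opens only for a dose in pregnancy. None of the seven modules has a trigger for a dose given after delivery.

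This is a data-collection rule fixed in the protocol, not an analysis choice that a statistical analysis plan could settle later. If the reaction questions are not put to people vaccinated in lactation, no analysis can supply the answers, and the lactation part of a primary objective could be reported only for events serious enough to lead to emergency care or admission.

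**Working it through.** **1. Which module each dose reaches, as written**

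| When the dose was given | Vaccine Outcomes | Health Event |
|---|---|---|
| During a pregnancy still in progress | Yes | Emergency visit or admission only |
| During a 2023 pregnancy that ended before enrolment | Unclear | Emergency visit or admission only |
| During lactation after the 2023 pregnancy | No | Emergency visit or admission only |

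The third row does not depend on how *current* is read, because a dose after delivery is not a dose during any pregnancy. Someone still nursing an older child while pregnant in 2023 would be routed, but by virtue of the pregnancy.

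**2. Whether another route fills the third row**

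- *Follow-up survey.* It would show that a postpartum dose was given. It then opens outcome modules according to their conditions, and the Vaccine Outcomes condition is still a dose in the current pregnancy.
- *Health Event.* It does not depend on pregnancy status or dose timing. It is limited to emergency visits and admissions, and it opens only through the two follow-up surveys.
- *Contact by the study team.* The protocol does not say how the team would learn of a reaction that needed no hospital care.

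**3. What kind of event is left without a route**

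Section 4.5 names ten event types as the basis for the sample size: injection-site pain, redness, swelling, fever, fatigue, chills, headache, muscle pain, joint pain and grade 4 serious events. The first nine are ordinary reactions that mostly do not lead to emergency care.

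The plan's figure reproduces. With p = 0.25, d = 0.04 and z = 1.96, n = z² × p(1 − p) / d² = 450.17, which rounds up to 451. That number is not in dispute. It matters here only because it shows which events the study was sized to measure.

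**4. Whether an ended pregnancy counts as current**

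The baseline routing sentence allows the pregnancy and vaccine outcome surveys to be answered together. Pregnancy Outcomes goes only to people who are no longer pregnant. Under a literal reading of *current*, nobody could receive both at baseline. That suggests the 2023 pregnancy is meant, whether or not it has ended, but the trigger does not say so.

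**5. Ceiling on who could be lactating within the survey period**

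Assumptions, not given in the documents: pregnancy starts uniform over the 365 days of 2023, and delivery at term. Counting 1 January 2023 as day 1, 1 February 2024 is day 397.

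- 266 days from conception: 397 − 266 = day 131 (11 May 2023), and 131/365 = 36%.
- 280 days from last menstrual period: 397 − 280 = day 117 (27 April 2023), and 117/365 = 32%.

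So about 32–36% of eligible pregnancies reach their due date by the last survey. This is a ceiling under these assumptions, because it counts people who do not breastfeed, people not vaccinated after delivery, and births just before the survey. Preterm births would raise it somewhat.

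**The case against.** The strongest reply is that the module list may be shorthand. The follow-up surveys decide when outcome modules are completed, and section 4.2 refers to data collection forms that are not shown. The actual branching could already include postpartum doses. That is possible, and it is why the finding is confined to the protocol as written. A protocol should still not state a narrower trigger than the one in use.

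Several stronger readings are tempting but not supported:

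- *No adverse events at all are collected after a lactation dose.* Health Event covers emergency visits and admissions whatever the dose timing, so the gap concerns ordinary reactions.
- *Reactions from pregnancies that ended before enrolment are lost.* The baseline routing sentence points the other way, so this is an ambiguity rather than a demonstrated loss.
- *Infant outcomes after lactation doses are blocked.* The reference to infants of women vaccinated in lactation shows that such doses are expected. Infant outcomes, however, belong to Pregnancy Outcomes, which opens once the pregnancy has ended.
- *Half the study population is affected, or the 451 is selectively eroded.* Naming two groups in an objective does not make them equal in size, and the documents give no share of doses outside pregnancy.

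It is also fair to say that the exposed time is limited. Under the assumptions in the last step of the working, time after term averages 131/365 × 65.5 = 24 days per participant, or 117/365 × 58.5 = 19 days. The mean time from pregnancy start to 1 February 2024 is 397 − 183 = 214 days, so the share is about 9–11%. This limits the size of the gap but does not remove it, because the objective names lactating people explicitly.

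**Conclusion.** The mismatch is on the face of the protocol. Objective 1 and the maternal safety endpoints include vaccination during lactation, while the stated trigger of Vaccine Outcomes excludes it. If the rule is followed as written, reactions that do not lead to emergency care or admission have no stated collection route after a lactation dose.

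The number of people affected cannot be derived from the documents. The 32–36% bounds the share of eligible pregnancies that could enter lactation by the last survey, assuming uniform starts and term delivery. It is not a share of participants vaccinated or of doses. Whether doses in a pregnancy that ended before enrolment open the module needs clarification and should not be counted as lost data.

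**What to change.** Redefine the Vaccine Outcomes trigger in section 4.2 as any COVID-19 vaccine dose since the start of the 2023 pregnancy, whether received during that pregnancy (ongoing or ended) or in later lactation. Apply it at baseline and at each follow-up survey. Record the dose date and whether the participant was pregnant or lactating at the time, and report adverse events separately for the two. The same wording settles the ended-pregnancy question.

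If reaction data in lactation are not intended, limit the lactation part of objective 1 to the emergency visits and hospitalisations that are collected.

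The cost is one branching condition in the survey database, one line of protocol text, and a few more participants answering a module that already exists.
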